9.2.4 Sample Size Determination

It is estimated from PK/PD modeling that the proportion of subjects treated with avatrombopag expected to achieve a platelet count of $\geq 100 \times 10^9/L$ on Procedure Day, when measured prior to platelet transfusion (if any), is approximately 85%. Assuming the true response rate is 0.8 and the desired lower boundary of the 2-sided 95% CI is at least 0.65, 60 enrolled subjects will provide greater than 90% power. If the decision is made to increase the dose of study drug at one of the interim reviews of the data based on the pre-defined boundaries, up to an additional 30 subjects may be enrolled in the study for a maximum sample size of 90 subjects.

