It is estimated from pharmacokinetic/pharmacodynamic modeling that the proportion of subjects treated with avatrombopag expected to achieve a platelet count of $\geq 100 \times 10^9/L$ on Procedure Day, when measured prior to platelet transfusion (if any), is approximately 85%. Assuming the true response rate is 0.8 and the desired lower boundary of the 2-sided 95% CI is at least 0.65, 60 enrolled subjects will provide greater than 90% power. If the decision is made to increase the dose of study drug at one of the interim reviews of the data based on the pre-defined boundaries, up to an additional 30 subjects may be enrolled in the study for a maximum sample size of 90 subjects.

SITES: Approximately 30 sites in the United States

SPONSOR:

Dova Pharmaceuticals
[name]
[name]
United States
[contact]
[contact]

TABLE OF CONTENTS

Signature Page	2
Investigator Agreement.....	3
Synopsis	4
Table of Contents.....	8
List of Tables	12
List of Abbreviations and Definition of Terms.....	13
1 Introduction and Background Information	14
1.1 Thrombocytopenia	14
1.2 Avatrombopag.....	14
1.3 Nonclinical Studies	15
1.4 Clinical Studies	15
1.4.1 Phase 1 Studies.....	15
1.4.2 Phase 2 Studies.....	16
1.4.3 Phase 3 Studies.....	17
1.5 Rationale.....	18
1.6 Risk/Benefit.....	19
2 Study Objectives	20
2.1 Primary Objective	20
2.2 Secondary Objectives.....	20
3 Study Description.....	21
3.1 Summary of Study Design	21
3.2 Study Indication	21
4 Selection and Withdrawal of Subjects	22
4.1 Inclusion Criteria.....	22
4.2 Exclusion Criteria.....	22
4.3 Withdrawal Criteria.....	24
4.3.1 Subjects with Study Drug Interruption or Discontinuation.....	24
5 Study Treatments	25
5.1 Treatment Groups.....	25
5.2 Rationale for Dosing	25

5.3	Randomization and Blinding.....	25
5.4	Breaking the Blind	25
5.5	Drug Supplies.....	26
5.5.1	Formulation and Packaging.....	26
5.5.2	Study Drug Preparation and Dispensing.....	26
5.5.3	Study Drug Administration.....	26
5.5.4	Treatment Compliance	26
5.5.5	Storage and Accountability.....	26
5.6	Prior and Concomitant Medications and/or Procedures.....	26
5.6.1	Excluded Medications and/or Procedures.....	26
5.6.2	Documentation of Concomitant Medication Use.....	27
6	Study Procedures	28
6.1	Informed Consent.....	28
6.2	Screening.....	28
6.2.1	Visit 1 – Screening Visit (optional).....	28
6.2.2	Visit 2 - Baseline Visit	28
6.3	Treatment Period.....	29
6.3.1	Visit 3	29
6.4	Visit 4 - Procedure Day.....	30
6.5	Follow-Up Period.....	30

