5.2 Rationale for Dosing

A PK/PD model was developed to simulate platelet response to avatrombopag administration in order to select a dose regimen for this study. Using data from healthy volunteers and patients with chronic liver disease, the PK/PD model evaluated the relationship of avatrombopag concentrations to increases in platelet counts. Simulations were performed assuming the baseline platelet count ranged between 50 and $<100 \times 10^9/L$ with a requirement to increase the platelet count to levels $\geq 100 \times 10^9/L$ prior to the procedure. Simulations suggested that 60 mg avatrombopag administered once daily for 5 days with the procedure scheduled 5 to 8 days after the last dose of study drug would result in approximately 85% of subjects having platelet counts that exceed $100 \times 10^9/L$. Simulations were also performed for subjects with CLD. In order to limit the number of subjects with a platelet count $>200 \times 10^9/L$ after treatment yet still have the majority of subjects with a platelet count $\geq 100 \times 10^9/L$ on the day of surgery, subjects with CLD must have a platelet count between 50 and $<75 \times 10^9/L$ at Baseline.

To ensure the accuracy of the predictions, platelet response data will be reviewed by the Sponsor and Medical Monitor, and if necessary, the Investigators participating in the study, after the enrollment of 25% and 50% of subjects to determine if the dose for subsequent subjects enrolled in the study should be increased to 80 mg once daily for 5 days.

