9.2.1.1 Primary efficacy analysis

The primary efficacy endpoint is the proportion of subjects achieving a platelet count of $\geq 100 \times 10^9/L$ on Procedure Day, when measured prior to a platelet transfusion (if any). Subjects with missing information due to early withdrawal or other reasons are considered as having a platelet count $< 100 \times 10^9/L$ in the analysis; that is, missing values are considered as non-responders. The primary endpoint will be estimated from a binomial distribution, with 95% confidence interval (CI) of the proportion calculated. The study will be claimed successful if the lower boundary of the 2-sided 95% CI is above the 0.65. The primary analysis will be performed on the FAS and repeated on the PPS.

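### The claim of more than 90% power with 60 subjects at a true response rate of 0.8 is wrong: the success rule has about 69% power, or 79% with the most lenient interval

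*Protocol*

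**What the plan says.** Section 9.2.1.1 of the protocol sets the success criterion: "The study will be claimed successful if the lower boundary of the 2-sided 95% CI is above the 0.65". On how the interval is formed it says only "The primary endpoint will be estimated from a binomial distribution, with 95% confidence interval (CI) of the proportion calculated", so the type of interval is not named.

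Section 9.2.4 justifies the sample size against this criterion. It reports the PK/PD prediction of roughly 85% responders, which section 5.2 also gives (the 60 mg regimen "would result in approximately 85% of subjects having platelet counts that exceed" the target). It then bases the power statement on a lower planning rate of 0.8, for which it claims that if "the desired lower boundary of the 2-sided 95% CI is at least 0.65, 60 enrolled subjects will provide greater than 90% power". The sample size paragraph of the synopsis repeats that "60 enrolled subjects will provide greater than 90% power". Up to 30 further subjects, for a maximum of 90, may be added only if the dose is raised after an interim review.

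**The concern.** The power sentence is complete. It gives the true rate (0.8), the threshold (0.65), the interval (2-sided 95%), the number of subjects (60) and the resulting power (above 90%), so it can be checked directly.

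A rough check already fails. At a true rate of 0.8 the standard error of the observed proportion with 60 subjects is √(0.8 × 0.2/60) = 0.0516. The distance from 0.8 to 0.65 is 0.15, or 2.9 standard errors. Power of 90% with a 2-sided 95% interval needs about 1.96 + 1.28 = 3.24.

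This sentence is the protocol's only quantitative support for 60 subjects against its formal success criterion. If it is wrong, anyone relying on the protocol has a mistaken view of how likely the study is to miss its primary criterion when the drug performs as assumed.

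**Working it through.** **Inputs** (sections 9.2.4 and 9.2.1.1): n = 60; true rate p = 0.80; success if the lower limit of the 2-sided 95% interval exceeds 0.65; missing counts are non-responses, so the denominator stays at 60. The interval type is not stated, so several were tried.

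**Step 1: smallest number of responders that meets the criterion.** The Clopper-Pearson lower limit for x responders is the 0.025 quantile of a Beta(x, n − x + 1) distribution. The Wald limit is x/n − 1.96 × √[(x/n)(1 − x/n)/n].

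| Responders of 60 | Clopper-Pearson | Wilson | Jeffreys | Wald |
|---|---|---|---|---|
| 44 (73.3%) | 0.603 | 0.610 | 0.612 | 0.621 |
| 45 (75.0%) | 0.621 | 0.628 | 0.631 | 0.640 |
| 46 (76.7%) | 0.640 | 0.646 | 0.649 | **0.660** |
| 47 (78.3%) | **0.658** | **0.664** | **0.667** | 0.679 |

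Bold marks the first value above 0.65. The Agresti-Coull, mid-P and logit intervals, and the continuity-corrected Wilson and Wald intervals, also need 47. Only the uncorrected Wald interval accepts 46. No limit equals 0.65 exactly, so the difference between the two sections (at least 0.65, or above 0.65) has no effect.

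**Step 2: power.** Power is P(X ≥ r) for X ~ Binomial(60, p). The false-positive rate is the same probability at p = 0.65.

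| Rule | Power at 0.80 | Power at 0.85 | False-positive rate at 0.65 |
|---|---|---|---|
| at least 47 (exact and most others) | 69.4% | 94.2% | 1.8% |
| at least 46 (Wald) | 79.3% | 97.1% | 3.6% |
| at least 45 | 86.9% | 98.6% | 6.6% |
| at least 44 | 92.3% | 99.4% | 11.0% |

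To exceed 90% at 0.80, 44 responders would have to count as success. All the lower limits at 44 are well below 0.65, and the false-positive rate of 11.0% is far above the 2.5% that a 2-sided 95% interval implies.

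**Step 3: attempts to reproduce the stated figure with approximate formulas** (n = 60, p = 0.80).

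Standard error under 0.80: 0.0516. Standard error under 0.65: √(0.65 × 0.35/60) = 0.0616.

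- Wald form: Φ(0.15/0.0516 − 1.96) = 82.8%.
- Score form: Φ[(0.15 − 1.96 × 0.0616)/0.0516] = 71.5%.
- Null variance throughout: Φ(0.15/0.0616 − 1.96) = 68.3%.
- Arcsine: 74.7%.

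None reaches 90%. The Wald formula with a one-sided 5% level gives 89.6%, but that is not the stated rule and is still below 90%.

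**Step 4: what would give 90%.**

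- With 60 subjects, the true rate would have to be about 0.837 under the 47-responder rule, or about 0.823 under the 46-responder rule.
- At a true rate of 0.80, the exact interval first reaches 90% at n = 96 (72 of 96, 90.9%) and stays there from n = 103. The Wald interval first reaches it at n = 79 and stays there from n = 86.
- At n = 90 and a rate of 0.80, the exact interval needs 68 responders and has 88.0% power. The Wald interval needs 67 and has 92.3%.

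**Step 5: is 0.8 the intended planning rate?** The interim boundaries in section 9.2.3 use 0.8, and their probabilities reproduce: P(X < 10 of 15) = 0.0611 and P(X < 21 of 30) = 0.0611. The planning rate is used consistently. Only the power figure does not follow from it.

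**The case against.** The best defence is that the interval type is left open and that cruder methods are kinder. That is partly true: 69% belongs to the exact interval, Wald raises true power to 79%, and the Wald approximation formula prints 83%. None of these exceeds 90%, so the choice of interval changes the size of the error and not its existence.

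A second defence is that the design can grow to 90 subjects. That expansion is tied to a dose increase, whereas the sentence concerns 60. Even at 90, the exact interval stays just below 90% at a rate of 0.80.

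A third is that the figure was meant for the PK/PD rate of 0.85, where it would be correct. That may be how it arose, but the protocol does not say so and ties the power to 0.8.

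Two limits on the criticism stand. First, because "missing values are considered as non-responders", the rate of 0.8 may already allow for subjects without a Procedure Day count. An allowance of about 6% would take 0.85 to 0.80 (0.85 × 0.94 = 0.80). No further deduction for missing data is therefore made here. Second, the error leaves the endpoint and success rule unchanged and does not inflate the false-positive rate, which is 1.8% with the exact interval. Leaving the interval type to the SAP would also be ordinary practice. It matters here only because the corrected power depends on it.

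**Conclusion.** The concern holds. For the inputs in section 9.2.4 the power is 69.4% with the exact interval and with every other interval tried except uncorrected Wald, which gives 79.3%. The risk of missing the success criterion at the planning rate is 31% (21% with Wald), against the less than 10% that the protocol implies. The result assumes independent responses at a common true rate of 0.80 that already counts missing values as failures, and all 60 subjects in the analysis. That the stated figure came from the 0.85 rate is a plausible guess, not something the document shows.

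**What to change.** Replace the power sentence in section 9.2.4 and in the synopsis with wording such as: *With 60 subjects, success requires at least 47 responders (lower limit of the exact 2-sided 95% confidence interval above 0.65). Power is about 69% if the true response rate is 0.80 and about 94% if it is 0.85.*

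Name the Clopper-Pearson interval in section 9.2.1.1 and the matching synopsis text, so that the restated power and the success rule refer to the same calculation: 46 of 60 succeeds under Wald and fails under the exact interval. If the sponsor prefers another interval, the responder count and power should be those of that interval.

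The cost is a few sentences of wording and a less favourable figure. Correcting the statement needs no extra subjects. Whether 69% power at 0.80 is acceptable is then for the sponsor to decide. If 90% at that rate is wanted with the exact interval, 96 subjects is the first size that gives it and 103 the size from which it is maintained.

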10 DATA MANAGEMENT AND RECORD KEEPING

10.1 Data Management

10.1.1 Data Handling

Data will be recorded at the site on eCRFs and reviewed by the Clinical Research Associate (CRA) on an ongoing basis and during monitoring visits. The CRAs will verify data recorded in the electronic data capture (EDC) system with source documents. All corrections or changes made to any study data must be appropriately tracked in an audit trail in the EDC system. An eCRF will be considered complete when all missing, incorrect, and/or inconsistent data has been accounted for and reconciliation between other databases (eg, safety, IRT) is complete.

10.1.2 Computer Systems

Data will be processed using a validated computer system conforming to regulatory requirements.

10.1.3 Data Entry

Data must be recorded using the EDC system as the study is in progress. All site personnel must log into the system using their secure user name and password in order to enter, review, or correct study data. These procedures must comply with Title 21 of the Code of Federal Regulations (21 CFR) Part 11 and other appropriate international regulations. All passwords will be strictly confidential.

10.1.4 Medical Information Coding

For medical information, the following thesauri will be used:

- Medical Dictionary for Regulatory Activities for medical history and adverse events, and
- World Health Organization Drug Dictionary for prior and concomitant medications.

10.1.5 Data Validation

Validation checks programmed within the EDC system, as well as supplemental validation performed via review of the downloaded data, will be applied to the data in order to ensure accurate, consistent, and reliable data. Data identified as erroneous, or data that are missing, will be referred to the investigative site for resolution through data queries.

The eCRFs must be reviewed and electronically signed by the Investigator.

10.2 Record Keeping

Records of subjects, source documents, monitoring visit logs, eCRFs, inventory of study product, regulatory documents, and other Sponsor correspondence pertaining to the study must be kept in the appropriate study files at the site. Source data is defined as all information in original records and certified copies of original records of clinical findings, observations, or other activities in a clinical study necessary for the evaluation and reconstruction of the clinical study. Source data are contained in source documents (original records or certified copies). These records will be retained in a secure file for the period as set forth in the Clinical Study Agreement. Prior to transfer or destruction of these records, the Sponsor must be notified in writing and be given the opportunity to further store such records.

11 INVESTIGATOR REQUIREMENTS AND QUALITY CONTROL

11.1 Ethical Conduct of the Study

Good Clinical Practice (GCP) is an international ethical and scientific quality standard for designing, conducting, recording, and reporting studies that involve human subjects. Compliance with this standard provides public assurance that the rights, safety, and wellbeing of study subjects are protected, consistent with the principles that have their origin in the Declaration of Helsinki, and that the clinical study data are credible.

11.2 Institutional Review Board

The IRB will review all appropriate study documentation in order to safeguard the rights, safety, and well-being of subjects. The study will only be conducted at sites where IRB approval has been obtained. The protocol, Investigator's Brochure, Informed Consent Form (ICF), advertisements (if applicable), written information given to the subjects, safety updates, annual progress reports, and any revisions to these documents will be provided to the IRB by the Investigator.

Federal regulations and International Council on Harmonisation (ICH) require that approval be obtained from an IRB prior to participation of subjects in research studies. Prior to study onset, the protocol, any protocol amendments, ICFs, advertisements to be used for subject recruitment, and any other written information regarding this study to be provided to a subject or subject's legal guardian must be approved by the IRB.

No drug will be released to the site until written IRB authorization has been received by the Sponsor.

11.3 Informed Consent

The ICF and any changes to the ICF made during the course of the study must be agreed to by the Sponsor or designee and the IRB prior to its use and must be in compliance with all ICH GCP, local regulatory requirements, and legal requirements.

The Investigator must ensure that each study subject (or legally authorized representative) is fully informed about the nature and objectives of the study and possible risks associated with participation and must ensure that the subject has been informed of his/her rights to privacy. The Investigator will obtain written informed consent from each subject (or legally authorized representative) before any study-specific activity is performed and should document in the source documentation that consent was obtained prior to enrollment in the study. The original signed copy of the ICF must be maintained by the Investigator and is subject to inspection by a representative of the Sponsor, their representatives, auditors, the IRB and/or regulatory agencies. A copy of the signed ICF will be given to the subject (or legally authorized representative).

11.4 Study Monitoring Requirements

It is the responsibility of the Investigator to ensure that the study is conducted in accordance with the protocol, Declaration of Helsinki, ICH GCP, and applicable regulatory requirements, and that valid data are entered into the eCRFs.

To achieve this objective, the monitor's duties are to aid the Investigator and, at the same time, the Sponsor in the maintenance of complete, legible, well organized and easily retrievable data. Before the enrollment of any subject in this study, the Sponsor or their designee will review with the

Investigator and site personnel the following documents: protocol, Investigator's Brochure, eCRFs and procedures for their completion, informed consent process, and the procedure for reporting SAEs.

The Investigator will permit the Sponsor or their designee to monitor the study as frequently as deemed necessary to determine that data recording and protocol adherence are satisfactory. During the monitoring visits, information recorded on the eCRFs will be verified against source documents and requests for clarification or correction may be made. After the eCRF data is entered by the site, the CRA will review the data for safety information, completeness, accuracy, and logical consistency. Computer programs that identify data inconsistencies may be used to help monitor the clinical study. If necessary, requests for clarification or correction will be sent to Investigators. The Investigator and his/her staff will be expected to cooperate with the monitor and provide any missing information, whenever possible.

All monitoring activities will be reported and archived. In addition, monitoring visits will be documented at the investigational site by signature and date on the study-specific monitoring log.

11.5 Disclosure of Data

Data generated by this study must be available for inspection by the FDA, the Sponsor or their designee, applicable foreign health authorities, and the IRB as appropriate. Subjects or their legal representatives may request their medical information be given to their personal physician or other appropriate medical personnel responsible for their welfare.

Subject medical information obtained during the study is confidential and disclosure to third parties other than those noted above is prohibited.

11.6 Retention of Records

To enable evaluations and/or audits from regulatory authorities or the Sponsor, the Investigator will keep records, including the identity of all participating subjects (sufficient information to link records, eg, eCRFs and hospital records), all original signed ICFs, copies of all eCRFs, forms for SAEs, source documents, and detailed records of treatment disposition. The records should be retained by the Investigator according to specifications in the ICH guidelines, local regulations, or as specified in the Clinical Study Agreement, whichever is longer. The Investigator must obtain written permission from the Sponsor before disposing of any records, even if retention requirements have been met.

If the Investigator relocates, retires, or for any reason withdraws from the study, the Sponsor should be prospectively notified. The study records must be transferred to an acceptable designee, such as another Investigator, another institution, or to the Sponsor.

11.7 Publication Policy

Following completion of the study, the data may be considered for publication in a scientific journal or for reporting at a scientific meeting. Each Investigator is obligated to keep data pertaining to the study confidential. The Investigator must consult with the Sponsor before any study data are submitted for publication. The Sponsor reserves the right to deny publication rights until mutual agreement on the content, format, interpretation of data in the manuscript, and journal selected for publication are achieved.

11.8 Financial Disclosure

Investigators are required to provide financial disclosure information to the Sponsor to permit the Sponsor to fulfill its obligations under 21 CFR Part 54. In addition, Investigators must commit to promptly updating this information if any relevant changes occur during the study and for a period of 1 year after the completion of the study.

12 STUDY ADMINISTRATIVE INFORMATION

12.1 Protocol Amendments

Any amendments to the study protocol will be communicated to the Investigators by [REDACTED] or the Sponsor. All protocol amendments will undergo the same review and approval process as the original protocol. A protocol amendment may be implemented after it has been approved by the IRB, unless immediate implementation of the change is necessary for subject safety. In this case, the situation must be documented and reported to the IRB within 5 working days.

APPENDIX A: SCHEDULE OF PROCEDURES

Table 1 Schedule of Procedures

Period	Screening		Treatment	Procedure Day	Follow-Up	
	1 (optional)	2 (Baseline Visit)	3	4	5	6 (ET Visit)
Day	Day -14 to -1	Day 1 [1]	Day 5	Day 10 [2]	7 Days Post-Procedure	Day 35
Window			(-2 days)	(+3 days)	(+3 days)	(±3 days)
Procedures						
Subject informed consent	X	X [11]				
Inclusion/exclusion criteria		X				
Demographics	X	X [11]				
Medical history [10]		X				
Concomitant medications		X	X	X	X	X
Adverse events	X	X	X	X	X	X
Physical examination [3]		X		X	X	X
Vital signs [4]		X		X	X	X
Hematology		X [5]	X	X	X	X
Platelet count [5]	X	X	X	X	X	X
Coagulation		X [5]	X	X	X	X
Serum chemistry		X		X	X	X
Pregnancy testing [6]		X [7]				X [7]
Assessment of platelet transfusion				X	X	X
Assessment of any rescue procedure for bleeding			X	X	X	X
Procedure-related information (type, risk, etc.)		X				
Contact IRT	X	X	X	X	X	X
Dispense study drug [8]		X				
Study drug dosing [8]		X	X			
Bleeding assessment (ISTH) [9]			X	X	X	X
Collect study drug				X		

Note: Prior to conducting any study-related activities, written informed consent must be signed and dated by the subject. Local laboratories will be used to determine eligibility; however, for study analysis and reporting purposes, only values determined at a central laboratory will be used with the exception of platelet count. Local laboratories may be used if immediate results are clinically needed.

1. All assessments will be performed prior to study drug dosing.

2. The following procedures will be performed pre-operatively on Procedure Day: vital signs, hematology, platelet count, coagulation, serum chemistry, record whether subject required a platelet transfusion, ISTH non-surgical bleeding assessment (if any bleeding), contact IRT, and collect study drug. The following procedures will be performed post-operatively on Procedure Day: concomitant medications, adverse events, record any rescue procedure for bleeding, and ISTH surgical bleeding assessment (if any bleeding).
 3. Physical examinations will consist of the following at a minimum: chest, lungs, heart, and abdomen.
 4. Vital sign measurements will include height (at the Baseline Visit only), weight, body temperature, blood pressure, and pulse rate and will be measured after resting for 5 minutes.
 5. Local and central laboratories. Baseline hematology, platelet count and coagulation laboratories may be collected up to one day prior to the Baseline visit (Visit 2).
 6. For female subjects of childbearing potential only. A serum or urine pregnancy test will be performed at the Baseline Visit prior to study drug administration.
 7. Either a serum or urine pregnancy test may be used.
 8. Subjects will receive 60 mg oral avatrombopag once daily for 5 days beginning on Day 1. For study site visits during the Treatment Period, study drug may be administered at the site or the subject may self-dose. Subjects will self-dose at all other times and be instructed to take study drug with food. The Investigator or designee will provide subjects with sufficient study drug to complete the 5-day regimen.
 9. Bleeding will be evaluated, if present, by the Investigator using the non-surgical and surgical ISTH bleeding definitions described in Appendix D. The non-surgical ISTH bleeding definitions (Table 3) will be used when evaluating subjects prior to surgery on Procedure Day, and the surgical ISTH bleeding definitions (Table 4) will be used when evaluating subjects after surgery on Procedure Day. Both the non-surgical and surgical ISTH bleeding definitions will be used to evaluate subjects during the Follow-up Period. For an Early Termination Visit where a subject withdraws from the study prior to surgery on Procedure Day, the non-surgical ISTH bleeding definitions will be used. If a subject withdraws after surgery on Procedure Day, both the non-surgical and surgical ISTH bleeding definitions will be used.
 10. Document etiology of thrombocytopenia.
 11. If Visit 1 not performed
- ET = Early Termination; IRT = Interactive Response Technology; ISTH = International Society on Thrombosis and Haemostasis.

